11.3.1 Adverse Events Definitions

For the purposes of this study, AEs include all ocular AEs/SAEs, and all non-ocular SAEs. Adverse events and SAEs are defined as follows.

An AE is any untoward medical occurrence, unintended disease or injury, or untoward clinical sign (including abnormal laboratory finding) in a subject, user, or other persons, whether or not related to the study treatment. For users or other persons, this definition is restricted to events related to the study treatment.

An SAE is an AE that leads to one or more of the following:

- Death
- A life-threatening illness or injury
- A permanent or significant disability/impairment of a body structure or body function (eg, blindness)
- In-patient or prolonged hospitalization
- Medical or surgical intervention to prevent life- or vision-threatening illness or injury or permanent impairment to a body structure or a body function

- Fetal distress, fetal death, or a congenital abnormality or birth defect

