7.3.4 Subject Discontinuation

A subject MUST be discontinued prior to the final study visit for any of the following reasons:

- Voluntary withdrawal
- Death
- Investigator decision that it is not in the best medical interest of the subject to continue participation in the study

A subject MAY be discontinued (at the discretion of the Investigator, the Sponsor, and/or the Institutional Review Board [IRB]) prior to the final study visit for several reasons, including but not limited to:

- Serious adverse event (SAE) and/or AE occurring during the course of the study that precludes continued follow-up
- Noncompliance with required study procedures
- Occurrence of a relevant exclusion criterion

Prior to discontinuing a subject from the study, every effort should be made to contact the subject, schedule a final study visit, and obtain as much follow-up data as possible. Whenever possible, subjects who have discontinued study treatment should be followed through the last scheduled study visit. Ongoing AEs will be followed as described in [Section 11.3.5](#). Subject withdrawals will be documented clearly on the source document and applicable Case Report Form (CRF). Subjects who discontinue from the study should be seen for routinely scheduled visits according to the standard of care by the Investigator or their ophthalmologist.

Notification of subject withdrawals will be made immediately to the Sponsor.

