11.3.2 Identification and Collection

Identification and collection of an AE begins after informed consent has been obtained and documented. Standard sources of identifying AEs include:

- Direct observation by the Investigator
- Asking the study participant a non-specific question (eg, “Have you had any problems since the last visit?”)
- Unsolicited volunteering of information by the study participant (eg, “Doctor, I have had blurred vision since I started using this lens.”)
- Test results that meet protocol requirements for classification as an AE

Specific to this protocol, ocular AEs and all SAEs (ocular and non-ocular) observed or elicited by the Investigator, reported by the subject, or resulting from a test result, etc., occurring during the clinical study must be reported on the CRF. During the study, the Investigator should treat the study subject as appropriate to ensure his/her safety and welfare. Refer to [Section 11.3.5](#) for additional information pertaining to ongoing AEs at subject exit.

Pre-existing conditions will not be considered AEs but will be collected at the Screening/Baseline Visit as medical history. A worsening of a pre-existing condition during the study should be documented as an AE and evaluated accordingly.

Hospitalizations for admission without a medical AE should be captured as an SAE until the cause of hospitalization can be identified. However, the following reports of hospitalization without a medical AE should not be considered either serious or an AE:

- Admission for treatment of a pre-existing condition not associated with the development of a new AE or with worsening of the pre-existing condition (eg, for work-up of persistent pretreatment lab abnormality)
- Social admission (eg, subject has no place to sleep)
- Administrative admission (eg, for yearly physical exam)
- Optional admission not associated with a precipitating medical AE (eg, for elective cosmetic surgery)

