12.3 Sample Size Determination

A sample size of 75 subjects will have 80% power to detect a difference in means of 8.194, assuming a standard deviation of differences of 25, using a paired t-test with a 5% two-sided

significance level. To allow for dropouts of up to 25%, approximately 100 subjects will be treated.

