12.5.2 Primary Effectiveness Analyses

12.5.3 Safety Analyses

12.5.3.1 Adverse Events

The number and percent of subjects with specific treatment-emergent adverse events (TEAEs) and the total number of occurrences of each TEAE will be summarized for the FAS. The number of subjects will be tabulated by Medical Dictionary for Regulatory Activities (MedDRA) system organ class and preferred term within each system organ class.

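### A non-serious, non-ocular event that makes a subject stop the drops or leave the study needs no AE record, so stopping because of AEs can be understated

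*Combined protocol and SAP*

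**What the plan says.** Section 11.3.1 sets the scope: "AEs include all ocular AEs/SAEs, and all non-ocular SAEs". It then gives a general definition with no such limit, which begins "An AE is any untoward medical occurrence, unintended disease or injury, or untoward clinical sign (including abnormal laboratory finding".

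Section 11.3.2 requires CRF reporting of "ocular AEs and all SAEs (ocular and non-ocular) observed or elicited by the Investigator", and likewise of those the subject reports or a test reveals. The same section says that a pre-existing condition which gets worse is to be documented as an AE, and does not confine that to the eye or to serious events. Section 11.3.4 gives a CRF route for non-serious events only if they are ocular. Section 11.3.3 asks for severity and relatedness when AEs are evaluated.

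Section 7.3.4 lists as a permitted ground for discontinuation: "Serious adverse event (SAE) and/or AE occurring during the course of the study that precludes continued follow-up". It also requires withdrawals to be documented in source and on the CRF, and asks that subjects who stop treatment be followed to the last visit where possible.

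On reporting, section 12.5.3.4 summarizes disposition and the reasons for leaving the study, without listing reason categories. Section 12.5.3.1 summarizes TEAEs on the FAS: "The number of subjects will be tabulated by Medical Dictionary for Regulatory Activities (MedDRA) system organ class", and by preferred term within class. It carries no statement of what was collected. The only planned split between ocular and non-ocular concerns concomitant medications (12.5.3.3).

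**The concern.** AEs are one of two safety outcomes in section 5.2.2; visual acuity is the other. In a two-week, single-arm study, an event that makes a subject give up the drops is among the more informative things that can be learned about tolerability. The collection rule sorts events by site and seriousness, not by consequence, so some of these events fall outside it.

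Two things are at stake. First, a reader of the final report may see that a subject stopped, through short exposure or low adherence, without any AE to explain it. Second, the TEAE table will have non-ocular classes filled mainly by SAEs. Without a label, few or no rows there could be taken as evidence that non-serious non-ocular events were rare, when they were not being collected.

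**Working it through.** **1. Follow one event through the plan.** Take a hypothetical subject with a new, non-serious headache that leads them to stop.

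- *AE record:* outside 11.3.1, outside the CRF list in 11.3.2, and without a route in 11.3.4. No AE CRF is required.
- *Severity and relatedness:* 11.3.3 applies to AEs, so neither is required.
- *If the subject leaves the study:* the withdrawal is documented (7.3.4) and its reason summarized (12.5.3.4). How the reason is coded is not stated.
- *If the subject stops the drops but attends Visit 4:* adherence (12.5.3.5) and last-dose date (12.5.3.6) show that dosing ended early. No readable section asks for the reason, and 12.5.3.4 covers only leaving the study.
- *TEAE table:* the event does not appear.

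If the same headache were the worsening of a pre-existing complaint, the sentence in 11.3.2, read literally, would have it documented as an AE. Two sites could treat similar events differently, and section 12.6.2 intends to pool the sites.

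**2. Does the scope touch the sample size?** Inputs from section 12.3: n = 75, difference 8.194, SD of differences 25, paired t-test, two-sided 5%.

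- Noncentrality = (8.194 / 25) × √75 = 0.32776 × 8.660 = 2.838, on 74 degrees of freedom.
- Power from the noncentral t = 0.79997, which reproduces the stated 80%.
- Dropout inflation: 75 / (1 − 0.25) = 100, which reproduces the stated number treated.

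The 25% allowance covers dropout from any cause, so the AE scope changes neither figure.

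**3. How many subjects could be affected?** The documents give no rate, so the risk p per subject of stopping for a non-serious non-ocular event is assumed. With 100 treated, the expected number is 100p and the chance of at least one is 1 − (1 − p)^100.

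| Assumed p | Expected subjects | Chance of at least one |
|---|---|---|
| 0.1% | 0.1 | 10% |
| 0.5% | 0.5 | 39% |
| 1% | 1 | 63% |
| 2% | 2 | 87% |
| 5% | 5 | 99% |

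**4. How sparse could the non-ocular classes be?** If they held only SAEs, with an assumed risk q per subject, the chance of none among 100 is (1 − q)^100: 90% at q = 0.1%, 61% at 0.5%, 13% at 2%. If a zero were taken as an observed rate for all events, its one-sided 95% upper bound would be 1 − 0.05^(1/100) = 2.95%. That bound would be warranted for SAEs, which are collected, but not for non-serious events, which generally are not.

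**The case against.** The strongest defence is that the restriction is deliberate, repeated and proportionate. It is stated in 11.3.1, repeated in 11.3.2 and consistent with 11.3.4. The product is an approved topical drop; the prescribing information in Appendix E reports low systemic blood levels, and the common adverse reactions it names are ocular. All SAEs are still collected, to 30 days after the last dose. This stands: nothing here argues for collecting every non-ocular event.

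It can also be said that withdrawals and their reasons are recorded whether or not an AE CRF exists, and that reason categories or table footnotes may be set in CRF instructions or in the statistical analysis plan to which 12.6.1 refers. This stands in part. It answers the case of a subject who leaves the study, apart from severity, relatedness and coding. It does not answer the case of one who stops treatment and stays in follow-up.

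A reader might go further and infer that AE-related dropout is certain to be miscounted. The documents do not support that. They plan no rate of discontinuation due to AEs, do not say how such a departure is coded, and keep a general definition under which a site could still give an AE as the reason. Nor does the allowance in 12.3 ("To allow for dropouts of up to 25" per cent) forecast AE withdrawals.

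A reader might also infer that the TEAE table will show an empty non-ocular section. No such section is planned, and non-ocular SAEs would appear, as might worsened pre-existing non-ocular conditions.

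**Conclusion.** The point holds as a gap in collection with a limited consequence. The plan requires no AE record for a non-serious, non-ocular event that ends treatment or participation. If the subject remains in follow-up, no readable section captures the reason for stopping. Attribution of stopping to AEs can therefore be understated. Total dropout, the 75 evaluable subjects and the 100 treated are unaffected.

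The size cannot be derived from the documents. Under the assumed range of 0.1% to 5% it runs from practically nothing to about five subjects in 100. The conclusion assumes that CRF instructions and table shells outside the available text do not already close the gap. Separately, the restricted scope and the 11.3.2 rule on worsening conditions pull in different directions and need to be reconciled.

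**What to change.** 1. In 11.3.1 and 11.3.2, add to the collected events: *and any AE, ocular or non-ocular, that leads to discontinuation of study treatment or withdrawal from the study*. Record these on the existing AE CRF, so that severity and relatedness follow under 11.3.3, and align the wording of 11.3.4.
2. In 11.3.2, state whether the rule on worsening pre-existing conditions reaches non-serious non-ocular conditions, so that all sites apply the same scope.
3. Title or footnote the 12.5.3.1 table with the collection scope: ocular TEAEs, all SAEs, and AEs leading to discontinuation. Sparse non-ocular classes will then not be read as an observed low rate of non-serious events.

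The cost is one phrase, one clarifying sentence, a table label and a few more AE entries. The ocular focus and the sample size stay as they are. The collection change helps only from the time it is adopted; the table label can be added at any point before reporting.

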11.3.2 Identification and Collection

Identification and collection of an AE begins after informed consent has been obtained and documented. Standard sources of identifying AEs include:

- Direct observation by the Investigator
- Asking the study participant a non-specific question (eg, “Have you had any problems since the last visit?”)
- Unsolicited volunteering of information by the study participant (eg, “Doctor, I have had blurred vision since I started using this lens.”)
- Test results that meet protocol requirements for classification as an AE

Specific to this protocol, ocular AEs and all SAEs (ocular and non-ocular) observed or elicited by the Investigator, reported by the subject, or resulting from a test result, etc., occurring during the clinical study must be reported on the CRF. During the study, the Investigator should treat the study subject as appropriate to ensure his/her safety and welfare. Refer to [Section 11.3.5](#) for additional information pertaining to ongoing AEs at subject exit.

Pre-existing conditions will not be considered AEs but will be collected at the Screening/Baseline Visit as medical history. A worsening of a pre-existing condition during the study should be documented as an AE and evaluated accordingly.

Hospitalizations for admission without a medical AE should be captured as an SAE until the cause of hospitalization can be identified. However, the following reports of hospitalization without a medical AE should not be considered either serious or an AE:

- Admission for treatment of a pre-existing condition not associated with the development of a new AE or with worsening of the pre-existing condition (eg, for work-up of persistent pretreatment lab abnormality)
- Social admission (eg, subject has no place to sleep)
- Administrative admission (eg, for yearly physical exam)
- Optional admission not associated with a precipitating medical AE (eg, for elective cosmetic surgery)

11.3.3 Evaluations

When evaluating AEs, the Investigator must determine if the event is serious (refer to [Section 11.3.1](#) for criteria), assess the severity of symptoms, and determine the relationship of the event to study treatment, using the following guidelines:

Severity

- **Mild:** Subject awareness of a sign or symptom that is easily tolerated, requires no treatment, and does not interfere with subject's daily activities
- **Moderate:** Subject awareness of a sign or symptom which may be a low level of concern to the subject and may interfere with daily activities, but can be relieved by simple therapeutic care

- **Severe:** A sign or symptom that interrupts the subject's daily activity and requires systemic therapy or other treatment

Relationship to Study Treatment

- **Related:** There is at least a reasonable possibility the AE is related to the study treatment. Reasonable possibility means there is evidence to suggest either a causal relationship or association between the study treatment and the AE
- **Not related:** There is little or no reasonable possibility the AE is related to the study treatment. No reasonable possibility means there is no evidence to suggest either a causal relationship or association between the study treatment and the AE

11.3.4 Reporting

Actions required by Investigators for reporting non-serious ocular AEs are to record them on AE CRFs only. Neither expedited report to the Sponsor nor report to the IRB is required for non-serious AEs.

Any SAE must be reported to the Sponsor/Contract Research Organization (CRO), independent of the circumstance or suspected cause, within 24 hours from the time the event was reported to the Investigator. All SAEs experienced between the date of consent and 30 days after the last administered dose of study treatment must be reported to the Sponsor/CRO regardless of the relationship to the study treatment or protocol. For events occurring beyond the 30-day period after the last administration of study treatment or for any timeframe greater than 30 days deemed medically significant, only SAEs considered related to the study treatment should be reported promptly to the Sponsor/CRO.

Within 24 hours of notification, the Investigator will fax or email a completed SAE Form to the Sponsor and CRO contact listed below. For SAEs with fatal outcomes, a summary of available autopsy findings should be submitted as soon as possible.

Care should be taken to ensure that the subject's identity is protected (personal identifiers are redacted), and the date and subject identifier in the clinical study (ie, subject number) are clearly visible on every page/copy of source document provided to the Sponsor. For laboratory results, the laboratory normal ranges should be included.

Investigators should not wait to receive additional information before notifying the Sponsor/CRO of an SAE. If only limited information is initially available, follow-up reports are required.

The Investigator will notify their IRB in writing of any SAE in accordance with the IRB requirements. Sponsor or its designee will be responsible for submitting SAE reports to regulatory authorities based on applicable regulations. The CRO will be responsible to send a notification to all participating Investigators of any SAE that is unexpected and associated with the study. If the Investigator becomes aware of any new information regarding an SAE (eg, resolution, change in condition, or new treatment), a new SAE Form must be completed and faxed/mailed to the Sponsor/CRO within 24 hours. The original SAE Form is not to be altered. The report should be marked as a "follow-up report" and should describe whether the event has resolved or continues and how the event was treated.

Serious AEs that have previously been reported and that continue after the subject's discontinuation or completion of the study will be followed until their medical endpoints are determined or until no further change in the conditions is expected. The events and endpoints will be reported in writing by the Investigator to the CRO. Following the subject's discontinuation or completion of the study, for any timeframe thereafter deemed medically significant, any SAEs that are assessed as causally related to study treatment should also be reported to the Sponsor/CRO.

The contacts for reporting SAEs are:

[REDACTED]
[REDACTED]
[REDACTED]

Contact information for the CRO will be provided on the SAE Form.

11.3.5 Adverse Events at Subject Exit

Ongoing AEs will be followed until resolution, until no further change in the condition is expected (ie, event stabilized), or as dictated by standard of care. Documentation on the CRF of this follow-up is not required, although subject care should continue as appropriate.

11.3.6 Pregnancy

All female subjects of childbearing potential and male subjects with female partners of childbearing potential must use an effective method of birth control during the course of the study, in a manner such that risk of contraceptive failure is minimized.

Before enrolling a female subject of childbearing potential or a male subject with a female partner of childbearing potential, the Investigator must review the following information about study participation:

- Informed consent requirement
- Contraceptives in current use

By signing the ICF, the Investigator or designee asserts that he/she has discussed this information with the subject and provided appropriate counseling. Following the review of this information, the subject must sign the ICF to enroll in the study.

During the study, all female subjects of childbearing potential should be instructed to contact the Investigator immediately if they suspect they might be pregnant (eg, missed or late menstrual period).

If a subject or Investigator suspects that the subject may be pregnant prior to treatment, the study treatment must be withheld until the results of laboratory pregnancy testing are available. If pregnancy is confirmed, the subject is considered to be a screen failure, must not continue in the study, and must not receive study treatment. If pregnancy is suspected while the subject is receiving study treatment, the study treatment must immediately be withheld until the result of pregnancy testing is known. If pregnancy is confirmed, the study treatment will be permanently discontinued, and the subject and neonate will be followed until 30 days after the pregnancy comes to term.

Female subjects who become pregnant during the study will be followed until completion of pregnancy. Every effort will be made to obtain the health status of the mother and infant or fetus (in cases of miscarriage or therapeutic abortion) at term. Pregnancy itself is not considered an AE.

All confirmed pregnancies must be immediately reported to the Medical Monitor, Sponsor, and CRO contact within 24 hours of the Investigator's awareness of the pregnancy. All confirmed pregnancies must be reported via confirmed facsimile or email transmission and must be submitted on a Pregnancy Report Form to the Sponsor or designee within 24 hours of the Investigator's awareness of the pregnancy. A Pregnancy Report Form will be submitted to the Sponsor, both when pregnancy is confirmed, and 30 days after the delivery date. Information provided on the Pregnancy Report Form must include the outcome of the pregnancy and any complications occurring during the pregnancy or the delivery. If a pregnancy is associated with an SAE, an SAE Form should also be submitted to the Sponsor/designee and Medical Monitor within 24 hours of the Investigator's awareness. Abnormal pregnancy outcomes (eg, spontaneous abortion, fetal death, stillbirth, congenital anomalies, ectopic pregnancy) are considered SAEs.

The contacts for reporting pregnancies are:

[REDACTED]
[REDACTED] [REDACTED]

Contact information for the CRO will be provided on the Pregnancy Report Form.

12 Statistics

12.1 Study Endpoints

12.1.1 Efficacy Endpoints

12.1.2 Safety Outcomes

The safety outcomes are detailed in [Section 5.2.2](#).

12.2 Hypotheses

The null hypothesis (H_0) is that the mean difference between the dry eye symptom severity values on Day 7 and at baseline (μ) is equal to zero. The alternative hypothesis (H_1) is that the mean difference is not equal to zero.

$$H_0: \mu = 0$$

$$H_1: \mu \neq 0$$

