Protocol Number:	#937
Number of Clinical Sites:	Up to 8 clinical sites in the United States
Study Phase:	4
Primary Objective:	To evaluate early outcomes with Miebo treatment in subjects with dry eye disease (DED)
Overall Study Design:	
Structure:	
This single-arm, open-label, multicenter, prospective study will consist of 4 study visits in subjects with DED. Subjects who sign the informed consent form at the Screening/Baseline Visit (Visit 1; Day 1) will be enrolled in the study and screened for eligibility to participate in the study. [REDACTED]
 
[REDACTED]. Following subjects' confirmation of eligibility and at least 15 minutes after the completion of the Schirmer's test, site staff will instill the first dose of Miebo and dispense Miebo to subjects. [REDACTED]
 
[REDACTED]
 
Subjects will then commence at-home treatment with Miebo 4 times daily (QID) bilaterally and will continue this for approximately 14 days. At Visits 2, 3, and 4 (Days 3, 7, and 14, respectively), subjects will complete 1 [REDACTED] Follow-up Visit in the clinic at least 30 minutes and no longer than 4 hours post-dose.

Subject Duration:	This study consists of 4 study visits over a period of approximately 14 days.
Study Duration:	The entire duration of the study (from first subject first visit to last subject last visit) is expected to take approximately 5 months.

Dosage Instillation:	Site staff will instill the first dose of Miebo in the clinic at Visit 1. After that, subjects will self-administer Miebo QID bilaterally for approximately 14 days. The last dose prior to Visits 2, 3, and 4 will be instilled at least 30 minutes and no longer than 4 hours prior to the start of the visit.
Measures Taken to Reduce Bias:	Not applicable
Study Population Characteristics	
Number of Subjects:	Approximately 100 subjects will be treated with Miebo.
Condition/Disease:	Subjects with DED

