5.2 Endpoints

5.2.1 Efficacy

The primary efficacy endpoint is the mean change from baseline (CFB) in dry eye symptom severity at Visit 3 (Day 7 ± 1 day).

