6.1 Overall Study Design and Plan: Description

This single-arm, open-label, multicenter, prospective study will consist of 4 study visits in subjects with DED. Subjects who sign the informed consent form (ICF) at the Screening/Baseline Visit (Visit 1; Day 1) will be enrolled in the study and screened for eligibility to participate in the study. Subjects will be asked to complete an Early Outcomes Survey - Baseline Visit 1 (Pre-dosing) to obtain baseline data at the start of Visit 1, after Ocular Surface Disease Index Questionnaire administration. Following subjects' confirmation of eligibility and at least 15 minutes after the completion of Schirmer's test, site staff will instill the first dose of Miebo and dispense Miebo to subjects. Subjects will then complete 2 additional Early Outcomes Surveys - Baseline Visit 1 (Post-dosing) at 5 minutes and 1 hour post-dose.

Subjects will then commence at-home treatment with Miebo 4 times daily (QID) bilaterally and will continue this for approximately 14 days. At Visits 2, 3, and 4 (Days 3, 7, and 14, respectively), subjects will complete 1 Early Outcomes Survey - Follow-up Visit in the clinic at least 30 minutes and no longer than 4 hours post-dose.

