7.1 Subject Inclusion Criteria

This study will include subjects who meet all of the following inclusion criteria:

1. At least 18 years of age at the time of consent
2. Able to provide written voluntary informed consent

3. The same eye must satisfy the below inclusion criteria (a–e):
 - a. Subject-reported history of DED in at least 1 eye for at least 6 months prior to Visit 1
 - b. Tear film break-up time (TBUT) ≤ 5 seconds at Visit 1
 - c. Total corneal fluorescein staining (CFS) score ≥ 4 and ≤ 11 (ie, sum of inferior, superior, central, nasal, and temporal) according to the National Eye Institute (NEI) scale at Visit 1
 - d. Total MGD score ≥ 3 (range, 0–15)
 - e. Unanesthetized Schirmer's test I score ≥ 5 mm
4. Ocular Surface Disease Index ≥ 25 at Visit 1
5. Able and willing to follow instructions, including participation in all trial assessments and visits

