7.3.5 Lost to Follow-Up

Subjects who do not return for scheduled visits, as defined by the visit window, and cannot be contacted may be considered lost to follow-up. The Investigator will try at least twice to reach the subject by telephone and/or email and will send a follow-up letter by certified mail before

considering the subject lost to follow-up. All follow-up attempts will be documented and kept with the subject's source documentation, and the applicable CRFs will be completed. The date a subject will be considered lost to follow-up will be the date of the last completed visit.

Efforts shall be made to keep the number of subjects lost to follow-up to a minimum, below 10% of the number of subjects treated.

8 Treatment Plan

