10.1.2 Visit 2: Day 3 + 1 day

The following study measurements will be collected:

- Concomitant medication
- Adverse event query
- Early Outcomes Survey – Follow-up Visit
- Dosing diary review by dedicated team member

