12.5 Statistical Analysis

12.5.1 General Considerations

Summaries for continuous variables will include the sample size (n), mean, standard deviation, median, minimum, and maximum. Summaries for categorical variables will include frequencies and percentages. Missing safety data will not be imputed.

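### Does testing the Day 7 change against zero, with no control arm, leave the plan with an unsound primary conclusion?

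*Combined protocol and SAP*

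**What the plan says.** Section 12.2 sets a two-sided null hypothesis that "the mean difference between the dry eye symptom severity values on Day 7 and at baseline" equals zero. Section 5.2.1 matches it: "The primary efficacy endpoint is the mean change from baseline (CFB) in dry eye symptom severity at Visit 3". Section 5.1 gives the objective as evaluating early outcomes with treatment, and 4.2 describes the aim as early perception of, and satisfaction with, treatment. Sections 6.1, 8.1.2 and 8.2 are open about the design: one arm, no randomization, no masking. In the synopsis, the row "Measures Taken to Reduce Bias" is marked as not applicable.

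On data collection, 6.1 has subjects complete a pre-dose survey "to obtain baseline data at the start of Visit 1, after Ocular Surface Disease Index Questionnaire administration". Section 7.1 requires "Ocular Surface Disease Index ≥ 25 at Visit 1". At Visits 2 to 4 the survey is completed in the clinic, between 30 minutes and 4 hours after a dose (6.1). The Visit 2 list (10.1.2) names "Early Outcomes Survey – Follow-up Visit" after the concomitant medication and adverse event items. The corresponding Visit 3 item is blacked out.

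On reporting, 12.5.1 says: "Summaries for continuous variables will include the sample size (n), mean, standard deviation, median, minimum, and maximum". The body of 12.5.2, which would hold the primary analysis, is not readable in the public version.

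**The concern.** A test of change against zero has no comparator. Subjects know what they are taking and rate their own symptoms. They also enter only if a symptom index is high at the same visit that supplies the baseline, so some fall by Day 7 could be expected without any drug effect. The result nevertheless sits under the labels efficacy (5.2.1) and effectiveness (12.5.2), and the row on bias is left as not applicable.

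The survey's place in the visit seems to be fixed at baseline but not at follow-up, which could shift the primary score in a way that no later analysis could undo. The list of summary statistics also omits a confidence interval.

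At stake is a p-value below 0.05 being read as proof that the product relieved symptoms. For that reading, the 5% error rate holds only if the non-drug change is exactly zero.

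**Working it through.** **Inputs.** From 12.3: n = 75 evaluable, SD of differences 25, difference 8.194, paired t-test, two-sided 5%, up to 25% dropout, about 100 treated. From 7.3.5: loss to follow-up is to be kept "below 10% of the number of subjects treated", which gives 100 × 0.90 = 90 as a middle case.

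**1. The plan's own figure.** Standard error at n = 75: 25/√75 = 2.887. Non-centrality: 8.194/2.887 = 2.838. With 74 degrees of freedom the critical t is 1.993, and the non-central t gives power of 80.0%. Treated: 75/(1 − 0.25) = 100. Both figures reproduce.

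**2. Smallest observed mean change reaching p<0.05**, t(0.975, n−1) × 25/√n:

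| n | t | SE | Critical mean | Share of 8.194 |
|---|---|---|---|---|
| 75 | 1.993 | 2.887 | 5.75 | 70% |
| 90 | 1.987 | 2.635 | 5.24 | 64% |
| 100 | 1.984 | 2.500 | 4.96 | 61% |

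**3. Probability of rejection if the drug adds nothing.** The documents give no size for non-drug change, so the first column is an assumption:

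| Non-drug change (points) | n=75 | n=90 | n=100 |
|---|---|---|---|
| 0 | 5% | 5% | 5% |
| 2 | 11% | 12% | 12% |
| 3 | 18% | 20% | 22% |
| 5 | 40% | 47% | 51% |
| 8 | 78% | 85% | 89% |

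**4. What these figures mean.** The second table is the test's power curve with its horizontal axis renamed. A non-zero mean change from any cause is the stated alternative in 12.2, so these rejections are correct for that hypothesis. The 70% at n = 75 is also generic: a two-sided 5% test with 80% power has its critical value near 1.96/2.80 = 0.70 of the detectable difference.

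**5. Hypothesis against endpoint and objective.** Section 5.2.1 names a mean change from baseline, 12.2 tests that mean change, and 5.1 asks about early outcomes without naming a comparison. The three agree. No readable passage states that a rejection will be attributed to the product.

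**6. Survey order.** Three things would have to be known, and none can be read.
- *Whether the primary score comes from this survey.* Section 11.1 is blacked out.
- *Where the survey falls at Visit 3.* The item in 10.1.3, the follow-up survey row of Appendix A and the methods in Appendix B are blacked out or not shown.
- *Whether list order is binding.* Footnote 2 of Appendix A imposes an order on marked assessments, but whether it covers the follow-up survey is not visible. At Visit 1, 10.1.1 lists the adverse event query last, while Appendix A places it above visual acuity. Position in a list is therefore not a reliable guide to sequence.

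Putting the survey first at every follow-up visit, ahead of medication review, is also not shown to match baseline. Section 6.1 puts the baseline survey after the symptom index. In 10.1.1 the medication item precedes the two blacked-out entries before visual acuity. If those entries are the index and the survey, medication review comes first at baseline, as it does in the Visit 2 list, and moving the survey ahead of it would create a mismatch.

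**7. Confidence interval.** Section 12.5.1 is a general rule for summaries. An interval, if planned, would be expected in the primary-analysis text, which is not readable. Nothing can be concluded from its absence elsewhere.

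**The case for a change.** The best case for a change is that the labels go further than the objective. A study of early outcomes and satisfaction need not call its result efficacy, and no readable sentence limits the conclusion. The appended prescribing information describes saline-controlled symptom results at Days 15 and 57 only, so the documents hold no controlled reference for Day 7. Masking and randomization may not apply, but uniform collection of a self-reported score does. Collection order cannot be repaired once the data are in, and a change would cost only wording and one site instruction.

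Much of this stands as a caution for the reader. The inference is limited exactly as described, the index threshold at the baseline visit is a real route to regression to the mean, and the bias row could have said more. The step from there to a defect does not stand. The labels are headings, not claims, and the bias entry is consistent with the statements in 8.1.2 and 8.2. The case on collection depends on unreadable text, and it leaves aside that follow-up surveys are already tied to the clinic and to a post-dose window. Relabelling headings would leave every rate in the tables above where it is.

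**Conclusion.** No change to the plan follows. The design accepts a known limit openly: a positive result will mean that symptom scores changed from baseline by Day 7, and the plan as written supports that conclusion. The size of the interpretive gap is a critical mean change of 5.75 points at n = 75 (4.96 at n = 100), and a chance of rejection without any drug effect that runs from 5% to 89% across assumed non-drug changes of 0 to 8 points. These figures rest on the plan's SD of 25 and on values that the documents neither give nor rule out.

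A sentence in 12.2 saying that rejection means change from baseline would do no harm. An analyst writing the report would say the same without it, and it would alter no procedure, estimate or result. On survey order and the confidence interval, the blacked-out text prevents any finding. If order does prove to be unspecified, the sensible reading is to follow the baseline order at follow-up.
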